7.5 Efficacy Analysis for Exploratory Endpoints

As a general strategy, analyses of the exploratory efficacy endpoints will be presented for all participants in the Full Analysis Set.

7.5.1 Change from Baseline in NEWS-2

NEWS-2 will be administered daily for hospitalized participants. NEWS-2 total score will be calculated according to authors' instructions (Appendix B.1). For participants who get discharged from the hospital before Day 15, their last available NEWS-2 total score will be carried forward to Day 15.

Mean observed and mean change from baseline in NEWS-2 total score at Day 15 will be tabulated by treatment group. Additionally, the difference in the least-squares means and their standard errors adjusted for baseline NEWS-2 score, stratification factors, baseline WHO Ordinal Scale for Clinical Improvement score, and number of co-existing conditions will be tabulated. Corresponding 95% confidence interval of the difference between two least-squares means and p-value will also be reported.

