### 1.2 Schedule of Events

The schedule of events (SOE) for Study Part 1 and Part 2 is presented in Table 1.

Table 1 Schedule of Events (Study Part 1 and Study Part 2)

Study Day (All Study Days are calendar days.)	Screening a	Day 1 BL	Day 2 b	Day 3 b	Day 4	Day 5 b	Day 6 b	Day 7 b	Day 8 or EOT s	Day 15	Day 28	Day 60 EOS b
Window	36 hours a									±3 days	+2 days	+2 days
Informed consent	X											
Demographics	X											
Eligibility assessment	X											
Medical history c	X											
Height and weight for BMI d		×										
Randomization		×										
NEWS2 e.n.s , vital signs, COVID-19 severity and subjective symptoms of COVID-19 n.s	X	X	X	X	X	X	X	X	X	X	X	X
Record SpO 2 and supplemental oxygen, and type of ventilation, if applicable e,f,s	X	X	X	X	X	X	X	X	X	X	X	X
Complete physical examination (excluding GU)		X							X			
Targeted physical examination	X											
Study drug administration g		X	X	X	X	X	X	X	X			
Serum chemistry h, p		X	X	X	X	X	X	X	X			
Hematology and coagulation i, p		X	X	X	X	X	X	X	X			
D-dimer (central laboratory)		X			X				X			
CRP (central laboratory)		X			X				X			
Cardiac troponin (central laboratory)		X			X				X			
LDH (central laboratory) j		X			X				X			
Ferritin (central laboratory)		X			X				X			
NP swab for confirmation of SARS-CoV-2 with RT-PCR k (local site laboratory)	X					Pe	Per local SOC	C				

Schedule of Events (Study Part 1 and Study Part 2) Table 1

Study Day (All Study Days are calendar days.)	Screeninga	Day 1 BL	Day 2 b	Day 3 b	Day 4	Day 5 b	Day 6 b Day 7 b	Day 7 b	Day 8 or EOT	Day 15	Day 28	Day 60 EOS b
NP swab for confirmation of SARS-CoV-2 with RT-PCR k (central laboratory)		X			X				X	X	X	
PK sampling l (Part 1 Only)				X								
WHO Ordinal Scale for Clinical Improvement e,m,s	X	X	X	X	X	X	X	X	X	X	X	×
Chest X-ray						Per ]	Per local SOC					
AE assessment e,5	X	X	X	X	X	X	X	X	X	X	X	X
Prior and Concomitant medications e,r,s	X	X	X	X	X	X	X	X	X	X	X	X
SOFAe,o,s		X	X	X	X	X	X	X	X	X	X	X
Blood for exploratory tests (e.g., IL-6, tissue factor, MCP-1 and IP-10)		X							X			
Serum pregnancy test for females of childbearing potential	X											

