#### 6.3.2 Daily Assessments (Day 2 through Day 8)

It may not be possible to conduct all study visits in-person due to quarantine and other infection control measures. In case where in-person visits are not possible, telemedicine appointments should be conducted. If the participant is discharged home with study drug for self-administration, visits appropriate for the telemedicine platform are Days 2, 3, 5, 6, 7, and the EOS/Day 60 visit.

For telemedicine appointments, all data should be collected, and the following should be reviewed/discussed in detail with the participant: AEs, concomitant medication, clinical status, and hospital re-admission. Due to the blood and NP swab collection requirements for central laboratory testing on Days 4, 8, 15, and 28, these visits should be conducted in person, either at the stie or with a home visit. If neither is possible, then a telemedicine appointment combined with a home nursing appointment for blood and NP sample collection could be arranged.

Procedures to be performed and information to be collected on Day 2 through Day 8 include:

- NEWS2 (Appendix 2), vital signs, severity of the participant's COVID-19 (Appendix 4), and assessment for presence of subjective clinical signs and symptoms of COVID-19 will be assessed daily and include presence or absence of: fever, cough (productive or non-productive), sore throat, malaise, headache, muscle pain, gastrointestinal symptoms (i.e., nausea, vomiting, or diarrhea), shortness of breath (with or without exertion), and respiratory distress. This should be performed between 2-6 hours after first dose of the day with study drug. Assessments should be collected daily while hospitalized including any day after Day 8 that the participant remains in the hospital.
- Record daily SpO2 on room air and need for supplemental nasal cannula oxygen (including flow rate) if applicable. For patients on supplemental oxygen, SpO2 should be recorded with at least 30 continuous minutes oxygen. Also record any noninvasive ventilation (i.e., No/Yes; if yes designate type). For intubated patients record PaO2 and FiO2 values of the worst P-F ratio of the calendar day. Assessments should be collected daily while hospitalized including any day after Day 8 that the participant remains in the hospital.

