#### 6.4 Day 15 (±3 days), and Day 28 (+2 days) Assessments

Procedures to be performed and information to be collected on Day 15 and Day 28:

- NEWS2 (Appendix 2), severity of the participant's COVID-19 (Appendix 4), and assessment for presence of subjective clinical signs and symptoms of COVID-19 including presence or absence of: fever, cough (productive or non-productive), sore throat, malaise, headache, muscle pain, gastrointestinal symptoms (i.e., nausea, vomiting, or diarrhea), shortness of breath (with or without exertion), and respiratory distress. Assessments should be collected daily while hospitalized including any day after Day 8 that the participant remains in the hospital.
- Record SpO2 on room air and need for supplemental nasal cannula oxygen (including flow rate) if applicable. For patients on supplemental oxygen, SpO2 should be recorded with at least 30 continuous minutes of oxygen Also record any noninvasive ventilation (i.e., No/Yes; if yes designate type). For intubated patients record PaO2 and FiO2 values of the worst P-F ratio of the calendar day.
- NP swab confirmation of SARS-CoV-2 with RT-PCR (local site laboratory) per site SOC.
- NP swab for confirmation of SARS-CoV-2 with RT-PCR on Day 15 (±3 days), and Day 28 (+2 days) for central laboratory testing.
- WHO Ordinal Scale for Clinical Improvement score (Appendix 1) assessment should be collected/recorded daily and any time the WHO Ordinal Scale for Clinical Improvement score changes. The WHO Ordinal Scale for Clinical Improvement should

be recorded with the corresponding date and time of assessment (if unchanged) or with the date and time reflecting the numerical change in the score (if changed).

- Chest X-ray per local standard-of-care.
- AE assessment.
- All systemic concomitant medications (Section 7.4).
- SOFA score (to be performed only for participants who are admitted in the ICU; Appendix 3).

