#### 9.6 **Handling of Missing Data**

Missing efficacy assessments will be imputed using a multiple imputation method appropriate to the pattern of missingness. Details of the considered patterns and associated sensitivity analyses will be described in the Statistical Analysis Plan.

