#### 9.7 **Multiplicity Adjustment**

A hierarchical testing scheme is planned to preserve the familywise type I error of the study. If statistical significance of the primary efficacy endpoint is established, secondary efficacy endpoints will be tested in the following order:

- 1. Mean change from baseline (BL) in National Early Warning Score (NEWS2)
- 2. Mean number of days on rescue treatment (COVID-19 treatments that are approved under NDA or EUA) within 15 days after enrollment

The testing scheme will be halted at the first secondary endpoint that fails to establish statistical significance.

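### SAP 7.5.1 carries NEWS2 forward to Day 15 because a participant was discharged, not because the Day 15 score is missing, and has no rule for deaths

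*SAP*

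**What the plan says.** SAP 7.5.1 begins "NEWS-2 will be administered daily for hospitalized participants" and then sets the rule: "For participants who get discharged from the hospital before Day 15, their last available NEWS-2 total score will be carried forward to Day 15". The trigger is discharge before Day 15. The endpoint is change from baseline at Day 15. It is analysed in the Full Analysis Set (SAP 7.5) by adjusted least-squares means, with a confidence interval and a p-value.

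Both documents schedule the Day 15 score for everyone:

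- In the Protocol 1.2 schedule, the row that groups NEWS2 with "vital signs, COVID-19 severity and subjective symptoms of COVID-19" is marked at every visit, including Day 15. SAP Appendix A repeats this.
- Protocol 6.4 puts NEWS2 first under "Procedures to be performed and information to be collected on Day 15 and Day 28" and does not confine it to inpatients. The same list does confine SOFA to participants in the ICU.
- Protocol 6.3.2 says of Days 4, 8, 15 and 28 that "these visits should be conducted in person", with telemedicine plus home nursing as a fallback. The footnotes to SAP Appendix A also leave Day 15 among the in-person visits.

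On missing data, Protocol 9.6 says: "Missing efficacy assessments will be imputed using a multiple imputation method appropriate to the pattern of missingness". It leaves the patterns and sensitivity analyses to the SAP. SAP 10.1 plans only limited imputation for exploratory endpoints. The one death rule in the SAP's efficacy sections is censoring for time to discharge (7.4). Neither 7.5.1 nor 10.1 says what happens to NEWS2 when a participant dies before Day 15.

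**The concern.** Carry-forward is a device for filling a gap. For SOFA it has some rationale, because after baseline SOFA is collected only in the ICU. NEWS2 has no such planned gap: the Day 15 score is due from discharged participants too. A rule keyed to discharge can therefore put an older score in place of the measurement that the endpoint names. That would hide worsening or readmission between discharge and Day 15.

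Discharge is also the outcome that the drug is meant to bring forward. If it does, carried scores will be more frequent, and taken earlier, on ANA001 than on placebo.

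Deaths are left to the programmer. The text points to opposite treatments of the same outcome, depending on whether the participant had left hospital first.

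**Working it through.** **1. The plan's own figure.** The documents give no standard deviation, power or target difference for NEWS2. The only stated figure that shares inputs with this check is the Part 2 event count in Protocol 9.1.2: medians of 15 and 11 days, 85% power, two-sided 0.05. With hazard ratio 11/15 and the Schoenfeld formula, events = 4 × (1.960 + 1.036)² / (ln(11/15))² = 4 × 8.98 / 0.0962 ≈ 373.3, rounded up to 374. This matches the stated 374 (power 85.1%), so the medians are being used as the protocol uses them.

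**2. Share of participants under the carry-forward rule.** Assume exponential times and apply the Part 2 medians to Part 1. The share discharged by day t is 1 − 0.5^(t/median).

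| t | Placebo (median 15) | ANA001 (median 11) | Difference | Of 60 in Part 1 |
|---|---|---|---|---|
| 14 days | 1 − 0.5^(14/15) = 0.476 | 1 − 0.5^(14/11) = 0.586 | 0.110 | 30 × 1.062 ≈ 32 |
| 15 days | 1 − 0.5^(15/15) = 0.500 | 1 − 0.5^(15/11) = 0.611 | 0.111 | 30 × 1.111 ≈ 33 |

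So about half of the Day 15 values would fall under the rule, about 11 percentage points more often on ANA001.

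**3. Possible shift from carrying forward.** Let d be the carried score minus the true Day 15 score, assumed equal in everyone discharged. Each arm mean moves by (share × d), and the between-arm difference moves by (0.611 − 0.500) × d = 0.111d. The documents give no d. Over an assumed range of −3 to +3 points, the arm means move by up to 0.500 × 3 = 1.5 (placebo) and 0.611 × 3 = 1.8 (ANA001) points. The difference moves by −0.33 to +0.33. This sum leaves out any difference between arms in how old the carried scores are.

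**4. Deaths.** The NEWS2 maximum from SAP Appendix B.1 is 6 items × 3, plus 2 for oxygen, which is 20. If a death counted as 20 instead of having no value, one death would move a 30-patient arm mean by (20 − m)/30, where m is the survivor mean. For assumed m of 0 to 3 this is 20/30 = 0.67 down to 17/30 = 0.57 points. The documents give no mortality rate. With an assumed 5% against 10% mortality by Day 15 and the same survivor mean in both arms, omitting deaths leaves out 0.05 × (20 − m), which is 0.85 to 1.00 points. With equal mortality it leaves out nothing.

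**5. What the text implies by type of participant.**

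| Participant | Day 15 value under SAP 7.5.1, read literally |
|---|---|
| In hospital at Day 15, never discharged | Observed score |
| Discharged earlier, Day 15 score measured | Carried score |
| Discharged earlier, Day 15 score missing | Carried score |
| Discharged, then readmitted before Day 15 | Carried score, although daily inpatient scoring resumes |
| Died in hospital before Day 15, never discharged | No rule; no Day 15 value, so probably omitted |
| Discharged, then died before Day 15 | Carried score |

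**The case against.** The strongest reply is that the rule is only a gap-filler. The SAP speaks of the last available score, not the last one before discharge. NEWS2 is scheduled after discharge as well, so the last available score could be a post-discharge one, even that of Day 15 itself. SAP Section 8 plans no visit windows and analyses results by the visit reported, which suggests that a reported Day 15 score would be used. This reading is tenable, and a reader who infers that observed scores will certainly be discarded goes further than the text. But 7.5.1 does not state the gap-filling condition and describes NEWS2 as an inpatient measure. Two programmers could build different datasets from it.

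Other limits also stand:

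- **Deaths.** A reader might infer that the plan drops all deaths. The SAP is silent. Omission of in-hospital deaths is what a model of change would ordinarily do with no value, but it is an inference, and a death after discharge would not be dropped.
- **Part 2.** A reader might infer that this rule will govern a confirmatory test. SAP Section 1 limits the document to the end of Part 1, and no text extends the rule. In Part 1 NEWS2 is exploratory, with 30 participants per arm and no type I error adjustment, and Protocol 9.3 plans no formal inference.
- **Conflict with Protocol 9.6.** The SAP was written to protocol Version 4.0 and the protocol reviewed is Version 5.0, so the difference may partly reflect timing. The mismatch over the Day 15 score does not depend on this, because SAP 7.5.1 and SAP Appendix A are in the same document.
- **Size.** The 50% and 61% count participants under the rule, not values wrongly replaced. The death figures rest wholly on assumed mortality and survivor means, and compare two definitions of the outcome. Eligibility also excludes critical illness and patients not expected to live beyond 48 hours.

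**Conclusion.** The point holds as an ambiguity with a material literal reading. SAP 7.5.1 applies carry-forward by discharge status where the schedule provides a measurement. Taken at its word, it sets the Day 15 value for about 48–50% of placebo and 59–61% of ANA001 participants, given the planning medians and exponential times. The effect on the treatment comparison cannot be signed from the documents. It stays within about 0.33 points if carried scores are off by up to 3 points, equally in both arms. The missing death rule is a separate gap, worth about 0.6 points on a 30-patient arm mean per death if deaths were scored at the maximum. In Part 1 the consequence is confined to an exploratory endpoint. It would be more serious if the same wording were reused for Part 2, where Protocol 9.7 tests NEWS2 first among the secondary endpoints. The change is worth making because it is nearly free and uses data already scheduled.

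**What to change.** Amend SAP 7.5.1 as follows:

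1. Analyse the NEWS2 score from the reported Day 15 visit whenever it exists, whatever the discharge status. The schedule already allows ±3 days for that visit, so no new analysis window is needed and SAP Section 8 can stand.
2. Impute only when that score is missing, in line with Protocol 9.6. Keep last-value carry-forward at most as a sensitivity analysis.
3. State how deaths before Day 15 are handled, whether or not the participant had been discharged. Add one prespecified sensitivity analysis that gives them a worst outcome, either the worst score or the worst rank. NEWS2 has no category for death, so this is a convention and should be described as one.
4. Report the numbers observed, imputed and dead by arm.

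The cost is SAP wording, a little more analysis work and one stated convention for deaths. No new data collection is needed. A Part 2 SAP should start from the amended wording.

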7.5.2 Number of Days on COVID-19 Rescue Therapy

According to the protocol, participants are allowed to receive concomitant treatments during the course of the study per the standard-of-care at the investigational site. Some concomitant treatments (*e.g.*, treatments granted US FDA approval, Emergency Use Authorization or glucocorticoid therapy) may aid the cure of COVID-19. For the purpose of this analysis, medications that may have direct anti-viral effects or systemic effects on the acute inflammatory processes of the virus/COVID and are given more than 24 hours after study drug started and no more than 240 hours (10 days) after enrollment will be considered COVID-19 rescue therapy. All concomitant medications will be reviewed in a blinded fashion prior to the database lock by team members with appropriate background and training to identify concomitant treatment that may be considered COVID-19 rescue therapy.

Mean number of days on COVID-19 rescue treatment within 15 days after enrollment will be tabulated by treatment group. The difference in the least-squares mean and their standard errors adjusted for stratification factors, baseline WHO Ordinal Scale for Clinical Improvement score, and number of co-existing conditions will be tabulated. Corresponding 95% confidence interval of the difference between two least-squares means and p-value will also be reported.

Participants who do not require any COVID-19 rescue treatment during the study will be excluded from the analysis of this endpoint.

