#### 7.4.2 Permitted Therapies

Therapeutics approved by the FDA and listed in CDC guidelines, or FDA authorized medications (i.e., under emergency-use authorization program) to prevent or treat COVID-19 and offered by the respective study site as standard-of-care may be administered and must be meticulously documented as outlined above.

Specifically, patients who deteriorate such that they fulfill criteria for more severe COVID-19 (e.g., require mechanical ventilation or increased oxygen support) may receive all treatments and FDA approved or FDA authorized medications determined by the respective investigative site to constitute standard-of-care for the treatment of severe or critical COVID-19 and should remain in the study.

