#### 9.1 Determination of Sample Size

#### **9.1.1 Study Part 1**

60 participants (30 randomized to ANA001 and 30 to placebo) are anticipated to provide sufficient data to assess safety and tolerability of ANA001 in patients with moderate and severe COVID-19. The sample size is based on clinical consideration and is consistent with the size of other studies with similar objectives.

#### **9.1.2** Study Part 2

One study reported that subjects treated with placebo will have a median time to clinical improvement around 15 days (Beigel *et al.*, 2020). Treatment with ANA001 is expected to reduce median time to clinical improvement to 11 days. At least 374 recoveries must be achieved for a log rank test to have 85% power at a two-sided significance level of 0.05.

Assuming a 6 months accrual period and the last enrolled subject will be followed for 30 days, at least 376 subjects must be randomized in 1:1 ratio. That is, at least 188 subjects must be randomized to be treated with ANA001 and 188 subjects to be treated with placebo.

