4.2.2 Exploratory Efficacy Endpoints

The following are the exploratory efficacy endpoints of Part 1 of this study:

- Mean change from baseline in the NEWS-2 total score on Day 15
- Mean number of days on rescue treatment (COVID-19 therapies that are FDA approved or have emergency-use authorization) within 15 days after enrollment.
- Median time (in days) to resolution of subjective symptoms assessed by the Investigator to be potentially due to COVID-19 including: fever, cough (productive or non-productive), sore throat, malaise, headache, muscle pain, gastrointestinal symptoms (i.e., nausea, vomiting, or diarrhea), shortness of breath (with or without exertion), and respiratory distress
- Proportion of participants who's COVID-19 progresses to Severe or Critical within 15 days after enrollment
- Proportion of participants requiring ICU admission within 15 days after enrollment
- Mean change from baseline in SOFA score on Days 8 and 15
- Proportion of participants on Days 8 and 15 requiring:
 - Supplemental oxygen
 - High flow nasal cannula (HFNC) oxygen
 - Non-invasive positive pressure ventilation (NIPPV)
 - Mechanical ventilation
- Mean number of days on mechanical ventilation within 15 days after enrollment
- Mean number of oxygenation-free days within 15 days after enrollment

- Proportion of participants who achieve a score of 1 on the WHO Ordinal Scale for Clinical Improvement on Days 8 and 15
- Median time (in hours) to a 2-point improvement in the WHO Ordinal Scale for Clinical Improvement
- Incidence and severity of thromboembolic events within 15 days after enrollment
- Incidence of abnormal markers of inflammation to include CRP, IL-6, TF, MCP-1, and IP-10 on Day 8
- Mean change in viral load from baseline on Days 1, 4, 8, 15, and 28
- Median number of days to viral load undetectable by nasopharyngeal (NP) swab

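### SAP 7.5.2 (Part 1, exploratory) counts rescue days over 15 days but admits a therapy as rescue only up to 240 hours, so rescue first given between 240 h and 360 h contributes no days

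*SAP*

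**What the plan says.** SAP 4.2.2 lists the Part 1 exploratory endpoint as "Mean number of days on rescue treatment (COVID-19 therapies that are FDA approved or have emergency-use authorization) within 15 days after enrollment". Protocol Table 2 gives the same 15-day window. Neither sets an earlier cut-off for when a therapy must begin.

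SAP 7.5.2 then defines rescue for this analysis. A medication with possible direct antiviral or systemic anti-inflammatory effect counts only if it is "given more than 24 hours after study drug started and no more than 240 hours (10 days) after enrollment". The next paragraph returns to the longer window: "Mean number of days on COVID-19 rescue treatment within 15 days after enrollment will be tabulated by treatment group". The section closes: "Participants who do not require any COVID-19 rescue treatment during the study will be excluded from the analysis of this endpoint".

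The general definitions of rescue in SAP section 6 and protocol 7.4.3 carry no hour limits. Protocol 7.4.2 also allows treatment on deterioration at any time: "patients who deteriorate such that they fulfill criteria for more severe COVID-19 (e.g., require mechanical ventilation or increased oxygen support) may receive all treatments" that the site regards as standard of care.

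**The concern.** Two windows in one section disagree. Days are to be counted to day 15, but a therapy can enter the count only up to day 10. In the last third of the stated window no new rescue can be recorded, and the SAP gives no reason for the difference.

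The quantity computed is then not the quantity defined. Rescue days inside the stated window are left out. A participant who deteriorates late and is treated for the first time after day 10 may appear as someone with no rescue days, or may not appear at all.

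**Working it through.** **Inputs.** Upper limit for a medication to qualify: 240 h after enrollment (SAP 7.5.2). Counting window: 15 days after enrollment (SAP 4.2.2 and 7.5.2, protocol Table 2). Enrollment means randomization (protocol 5.2), taken as 0 h. The SAP gives no day-counting rule for this endpoint, so days are taken as elapsed hours divided by 24; that is an assumption.

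**The plan's own figure.** 240 / 24 = 10 days, as the SAP states.

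**The gap.** 15 × 24 = 360 h. 360 − 240 = 120 h = 5 days, and 120 / 360 = one third of the counting window. If calendar dates were counted inclusively, the gap could touch 6 dates.

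**Days for a single course running to 360 h or beyond.** Endpoint days = (360 − start) / 24. The word for administration in SAP 7.5.2 can mean that the therapy was started by 240 h, or that each administration fell by 240 h.

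| First given at | Days under the 15-day endpoint | Days under 7.5.2, limit on start | Days under 7.5.2, limit on each administration |
|---|---|---|---|
| 192 h | 168 / 24 = 7.00 | 7.00 | 48 / 24 = 2.00 |
| 239 h | 121 / 24 = 5.04 | 5.04 | 1 / 24 = 0.04 |
| 241 h | 119 / 24 = 4.96 | 0 | 0 |
| 264 h | 96 / 24 = 4.00 | 0 | 0 |
| 312 h | 48 / 24 = 2.00 | 0 | 0 |
| 336 h | 24 / 24 = 1.00 | 0 | 0 |

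The last four rows are 0 on both readings. On the start reading, two hours' difference in first administration (239 h against 241 h) separates about 5 days from none. The loss is smaller if an earlier qualifying therapy is still running, because the overlapping days are already counted.

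**What happens to a participant whose only rescue starts after 240 h.**
- If the exclusion sentence uses the timed definition in 7.5.2, the participant is a non-user and is excluded.
- If it is read by its reference to the whole study, or by the untimed definition in SAP section 6, the participant is a user and stays in with 0 days.

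Neither result equals the endpoint value, which is up to 5 days.

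**Effect of moving the limit to 360 h.** Counting stops at 360 h in any case, so the two readings now agree at the upper end: a course from 192 h gives 7 days on both, and one from 241 h gives 4.96 days on both.

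**What the move does not repair.** Assume an arm of 30 with 12 users averaging 8 days, to which k late starters averaging 2.5 days are added. The users-only mean is (12 × 8 + 2.5k) / (12 + k): 8.0 at k = 0, then 7.58, 6.90 and 6.38 at k = 1, 3 and 5. The mean over all 30 is (96 + 2.5k) / 30: 3.20, then 3.28, 3.45 and 3.62. With non-users excluded, more rescue use can lower the reported mean.

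**The case against.** The best defense is that the limit is deliberate. It is introduced as a rule for this analysis and given in both hours and days, so it is not a slip. A qualification window for starts can coexist with a longer window for counting days. That is possible, but no rationale is stated, and a deliberate 10-day limit would still contradict an endpoint defined over 15 days in SAP 4.2.2 and in 7.5.2 itself. The SAP was written to protocol Version 4.0, but this does not explain the conflict, because both windows stand in the SAP.

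Several stronger readings are tempting and are not supported:

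- **All rescue after day 10 is lost.** This holds only if the limit applies to each administration. The text does not settle that. Only therapy first given after 240 h is lost on both readings.
- **Late starters are dropped.** They may instead be kept with 0 days, as shown above.
- **The omission is large, because many participants are still in hospital at day 10.** With the Part 2 planning medians in protocol 9.1.2 (15 and 11 days) and an assumed exponential shape, 0.5^(10/15) = 63% and 0.5^(10/11) = 53% would be undischarged, about 19 and 16 of 30 per arm. That describes who could start late, not who does, and does not size the defect.
- **The treatment comparison is biased.** The same rule applies to both arms, rescue is identified blind, and no start-time data by arm are given.
- **The Part 2 secondary endpoint is affected.** Rescue days are in the Part 2 testing hierarchy (protocol 9.7), but this SAP covers Part 1 only.

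It is also fair to object that moving the limit does not make 7.5.2 match the stated endpoint in full. The 24 h lower limit and the broader drug-class wording remain departures from SAP 4.2.2 and protocol Table 2.

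**Conclusion.** The mismatch is certain from the text. A therapy first given between 240 h and 360 h adds no days to an endpoint defined to include that interval. The cost is up to 5 elapsed days per participant, assuming days are hours divided by 24 and no earlier qualifying therapy is still running. Whether a participant with only late rescue scores 0 or leaves the analysis is ambiguous as written. The number of such participants, and so the effect on the treatment difference, cannot be derived from the documents.

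Severity is minor. This is one exploratory endpoint in a part of "60 participants (30 randomized to ANA001 and 30 to placebo"), with no formal inference planned (protocol 9.3) and no type I error control (SAP section 9), although 7.5.2 does report a confidence interval and a p-value.

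**What to change.** In SAP 7.5.2:

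1. Change the upper limit from 240 hours (10 days) to 360 hours (15 days) after enrollment.
2. State that days on qualifying therapy are counted through 360 h.
3. Use the same rule in the exclusion sentence to decide who is a rescue user.

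Do not tie the 24 h lower limit to first administration as part of this change. With study drug started at 0 h, a therapy running from 20 h to 360 h is 340 / 24 = 14.2 days under the 15-day endpoint. It would count 0 if the lower limit applied to its first administration. Under the current text, read as applying to each administration, it counts (240 − 24) / 24 = 9 days. The lower limit, the drug-class wording and the exclusion of non-users each need their own decision.

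The cost is a few words in one section before Part 1 is unblinded. No new data are needed, because protocol 7.4 already requires start and stop dates and times for each medication. If the sponsor does intend a 10-day limit, the alternative is to give the reason and restate the endpoint in 4.2.2 and 7.5.2 to match.
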